
 
To perform a preliminary analysis of vaccine efficacy in the prevention of molecularly confirmed COVID-19
 
	
 
The number of molecularly confirmed COVID-19 cases in Ad26.COV2.S versus placebo recipients in the overall study
 

 
To perform preliminary analysis of vaccine efficacy in the prevention of asymptomatic SARS-CoV-2 infection
 
	
 
The number of participants with positive non-S protein ELISA (eg, N ELISA), if such an assay can be developed, in the Ad26.COV2.S and placebo groups
 

 
To evaluate the presence of SARS-CoV-2 infection and the presence and severity of COVID-19 signs and symptoms
 
	
 
Presence and severity of COVID-19 signs and symptoms
 
Confirmation of SARS-CoV-2 infection by molecular testing
 

 
To examine the immune response in vaccinated individuals after natural infection and to explore other potentially informative biomarkers (eg, those associated with more severe disease)
 
	
 
Confirmation of SARS-CoV-2 infection by molecular testing
 
SARS-CoV-2 neutralizing titers in serum measured by a VNA (wild-type virus and/or pseudovirion expressing S protein)
 
SARS-CoV-2-binding antibodies measured by ELISA: Analysis of antibodies binding to the SARS-CoV-2 S protein
 
Functional and molecular antibody characterization
 
Analysis of gene expression by RNA transcript profiling
 

 
To explore the immune responses in fine needle LNA in Cohort 1b participants
 
	
 
Magnitude, phenotype, antigen specificity and subset distribution of immune and stromal cells in lymph nodes and peripheral blood
 
Molecular network analysis of functional regulation of T- and B-cell subsets in lymph nodes
 

\* Excluding Group 5 (placebo only) participants who received a single dose of  $5 \times 10^{10}$  vp Ad26.COV2.S at the time of unblinding, after EUA or approval in any country and local approval of protocol Amendment 10.

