Following local approval of protocol Amendment 15, all eligible participants (see Section 8.7) will be offered a single ad hoc booster dose of  $5 \times 10^{10}$  vp Ad26.COV2.S. The ad hoc booster vaccination will be provided to participants who have previously received 1 or more doses of any COVID-19 vaccine (ie, the Ad26.COV2.S vaccine, an mRNA vaccine and/or another COVID-19 vaccine authorized for primary vaccination including protein, inactivated, and adenovector-based vaccines) if the last vaccination was  $\geq 6$  months ago. Participants who choose to receive an outside of the study booster vaccination with the Ad26.COV2.S vaccine (if recommended by local authorities and available) or another authorized COVID-19 vaccine, choose not to receive an ad hoc booster vaccination, or are not eligible to receive the ad hoc booster vaccination, will not be withdrawn from the study and will be encouraged to remain in the study. Refer to Section 8.7 for more details.

The study includes the following cohorts:

- 1) Cohort 1:
  - a. Cohort 1a: approximately 375 participants (75 participants per group) aged  $\geq 18$  to  $\leq 55$  years who will be randomized in parallel in a 1:1:1:1:1 ratio to 1 of 5 vaccination groups.
  - b. Cohort 1b: 25 participants (5 participants per group) aged  $\geq 18$  to  $\leq 55$  years who will be enrolled at the Beth Israel Deaconess Medical Center (BIDMC) and randomized in parallel in a 1:1:1:1:1 ratio to 1 of 5 vaccination groups. Additional exploratory immunogenicity evaluations (eg, epitope mapping, passive transfer, and certain analyses of functional and molecular antibody characteristics) will be performed for Cohort 1b. Optional fine needle LNA will be collected from consenting participants after their 2nd vaccination (active or placebo) or approximately 6 months after the ad hoc crossover vaccination (for participants who crossed over from placebo to receive active Ad26.COV2.S  $5 \times 10^{10}$  vp vaccination), to further explore the immune responses in lymph nodes (refer to Section 8.1.1.1 for more details).
- 2) Cohort 2: approximately 270 participants aged  $\geq 18$  to  $\leq 55$  years will be randomized to receive Ad26.COV2.S (approximately 240 participants) or a placebo (approximately 30 participants) in the primary regimen. Cohort 2 will include an evaluation of a single booster vaccination (see below for further details).

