### **Cohort 2 (Adults Aged $\geq 18$ to $\leq 55$ Years)**

Cohort 2 will be initiated after interim or primary analyses of Cohort 1a. In Cohort 2a, approximately 120 participants will receive Ad26.COV2.S at a dose level of  $5 \times 10^{10}$  vp and approximately 15 participants will receive a placebo in a single-dose primary regimen. In Cohort 2b, approximately 120 participants will receive Ad26.COV2.S at a dose level of  $5 \times 10^{10}$  vp and approximately 15 participants will receive a placebo in a 2-dose primary regimen. No staggered enrollment will be performed for Cohort 2; however, the DRC will evaluate safety data from Cohort 2 over the course of the study. If required, Cohort 2 may contribute to the safety database prior to initiation of larger studies.

If the immunogenicity results obtained after the 1st vaccination in Cohort 1a are not adequately supporting initiation of Cohort 2, then results obtained after the 2nd vaccination in the 2-dose regimens in Cohort 1a will be used to select the vaccine regimens to be evaluated in Cohort 2 of

this study. If the immunogenicity results obtained after the 2nd vaccination in the 2-dose regimens in Cohort 1a do not demonstrate an adequately increased immune response, the sponsor will not provide the 2nd vaccination at Day 57 in Cohort 2b of this study. The immunogenicity results available from Cohort 1a supported the administration of the 2nd vaccination at Day 57 in Cohort 2b.

In addition, data obtained after a single booster vaccination will be used to evaluate the effect of a booster vaccination at different time points and the duration of immune response (see below for further details).

[figure not shown]

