Participants with comorbidities that are or might be associated with an increased risk of progression to severe COVID-19a, ie, participants with moderate-to-severe asthma; chronic lung diseases such as chronic obstructive pulmonary disease (COPD) (including emphysema and chronic bronchitis), idiopathic pulmonary fibrosis and cystic fibrosis; diabetes (including type 1 or type 2); serious heart conditions, including heart failure, coronary artery disease, congenital heart disease, cardiomyopathies, and (pulmonary) hypertension or high blood pressure; obesity (BMI  $\geq 30$  kg/m^2); chronic liver disease, including cirrhosis; sickle cell disease; thalassemia; cerebrovascular disease; neurologic

---

aPer US CDC (See Section 10.10, Appendix 10). Gestational diabetes was deleted from the list since it is not applicable as pregnant women are not allowed to participate in the study.

conditions (dementia); smoking; end stage renal disease; organ transplantation; cancer; HIV infection and other immunodeficiencies; hepatitis B infection; and sleep apnea.

Applicable to Cohort 3 only: Participants may have hypertension of mild severity (according to the Toxicity Grading Scale in Section 10.6, Appendix 6), as long as it is stable and medically controlled as defined by no change in medication over the past 6 months (except for issues of tolerability or use of similar drug with same mechanism of action, eg, thiazides, Beta blockers, Alpha blockers at the same effective dose).

24. Criterion added per Amendment 1:

24.1 Criterion modified per Amendment 3:

Applicable to Cohorts 1 and 3 only: Participant currently working in an occupation with a high risk of exposure to SARS-CoV-2 (eg, health care worker or emergency response personnel) or considered at the investigator's discretion to be at increased risk to acquire COVID-19 for any other reason.

25. Criterion added per Amendment 3:

History of confirmed COVID-19 or known exposure to an individual with confirmed COVID-19 or SARS-CoV-2 infection within the past 2 weeks (Not applicable for the seropositive participants).

26. Criterion added per Amendment 3:

History of confirmed SARS or MERS.

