## **7. DISCONTINUATION OF STUDY VACCINATION AND PARTICIPANT DISCONTINUATION/WITHDRAWAL**

### **7.1. Discontinuation of Study Vaccination**

Study vaccinations will be withheld for the reasons listed below. These participants must not receive any further doses of study vaccine but should remain on study for follow-up with assessments of safety and immunogenicity. Additional unscheduled visits may be performed for safety/reactogenicity reasons, if needed. In case of questions, the investigator is encouraged to contact the sponsor.

- Any related AE, worsening of health status or intercurrent illnesses that, in the opinion of the investigator, requires discontinuation from study vaccine
- The participant becomes pregnant
  - Note: Applicable to the US only: Following local approval of Protocol Amendment 15, participants who are pregnant may receive booster vaccination with Ad26.COV2.S, if allowed by local regulations and if the investigator considers that the potential benefits outweigh the potential risks to the mother and fetus (see Section 8.7).
- Unblinding on the participant level that, in the opinion of the sponsor, would compromise the integrity of the data
- The participant received an authorized/licensed COVID-19 vaccine outside of the study.
  - Note: following local approval of protocol Amendment 15, eligible participants (see Section 8.7) are allowed to receive a single ad hoc booster dose of Ad26.COV2.S vaccine ( $5 \times 10^{10}$  vp) if the last vaccination was  $\geq 6$  months ago.
- Anaphylactic reaction following vaccination, not attributable to causes other than vaccination
- SAE or other potentially life-threatening (Grade 4) event that is determined to be related to study vaccine
- Chronic or recurrent use of systemic corticosteroids and administration of antineoplastic and immunomodulating agents or radiotherapy
- Withdrawal from further study vaccination
- Participant has a positive test result for SARS-CoV-2 infection during the study (see Section 8.1.2). Note: participants may receive a placebo crossover vaccination or ad hoc booster vaccination with the Ad26.COV2.S vaccine after they have recovered from the acute illness and at least 3 months have passed as specified in Sections 8.6 and 8.7.
- Participant receives any experimental medication (including experimental vaccines other than the study vaccine) or receives a COVID-19 treatment
- Participant previously experienced TTS, or heparin-induced thrombocytopenia (HIT) or GBS.

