- Participants should complete the SIC (see Section 10.7, Appendix 7, Symptoms of Infection with Coronavirus-19 [SIC]) and record their highest body temperature daily starting on the first day they experience symptoms. If either nasal swab is positive for SARS-CoV-2 or influenza, collection of data will continue until sign and symptom resolution. If the first nasal swab is negative, collection of data will continue until the negative test is confirmed by the second nasal swab or until sign and symptom resolution, whichever comes first. Long-term sequelae of COVID-19 (eg, anosmia, headache, fatigue, and other symptoms at the investigator's judgement) will not be followed until their resolution if not resolved within a month.
- For participants with a positive test result for SARS-CoV-2 infection, a study visit will be conducted 28 days after symptom onset to assess the clinical course of the infection, record concomitant medications since symptom onset, and obtain a blood sample for assessment of the humoral immune response (VNA, ELISA, and Fc functionality) and other biomarkers (RNA-seq).

If a participant has a positive test result for SARS-CoV-2 infection, the participant may be requested to remain at home and not visit the study site. If necessary, study-site personnel will visit the participant at home. Under these circumstances, the participant will be contacted by the site at least once per week and the participant's medical care provider will be notified. The participant will not receive further study vaccinations but should remain on study for follow-up with assessments of safety and immunogenicity (see section 7.1), unless they withdraw consent from the study (see section 7.2). The participant will be followed until resolution of clinical symptoms (except for long-term sequelae of COVID-19).

The sponsor recommends to follow these participants until 2 consecutive negative nasal swabs could be obtained.

If a participant has a positive test result for influenza infection, study visits will continue per the [Schedule of Activities \(SoA\)](#).

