### **9.3. Populations for Analysis Sets**

For purposes of analysis, the following populations are defined:

**FAS:** The full analysis set will include all participants with at least one vaccine administration documented.

**PPIa:** The per protocol immunogenicity population will include all randomized and vaccinated participants for whom immunogenicity data are available excluding participants with major protocol deviations expecting to impact the immunogenicity outcomes. In addition, samples obtained after missed vaccinations or from participants with natural infection occurring after screening (if applicable) will be excluded from the analysis.

**PPE:** The per protocol efficacy population will include all randomized participants having received at least 1 vaccination for whom efficacy data concerning endpoint measures are available. All efficacy analyses will be done according to the as treated principle (ie, actually received vaccinations).

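### The exploratory efficacy comparison pools cohorts randomised 4:1 and 8:1 without naming cohort strata, so it is confounded by cohort if cohort risks differ

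*Protocol*

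**What the plan says.** Section 3 lists, as an exploratory objective, a preliminary analysis of efficacy against molecularly confirmed COVID-19. Its endpoint is "The number of molecularly confirmed COVID-19 cases in Ad26.COV2.S versus placebo recipients in the overall study".

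Allocation differs by cohort (Section 4.1, Table 1). Participants in Cohorts 1a, 1b and 3 are those "who will be randomized in parallel in a 1:1:1:1:1 ratio to 1 of 5 vaccination groups". Only Group 5 is placebo throughout, which gives 4 active to 1 placebo. Cohort 2 participants are "randomized to receive Ad26.COV2.S (approximately 240 participants) or a placebo (approximately 30 participants) in the primary regimen", which is 8 to 1. Section 6.3 states that randomisation takes place within each cohort.

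The cohorts also differ in who is enrolled and when:
- Exclusion criterion 24 (Section 5.2) reads "Applicable to Cohorts 1 and 3 only: Participant currently working in an occupation with a high risk of exposure to SARS-CoV-2". Cohort 2 has no such exclusion.
- Cohort 3 is aged 65 and over; Cohorts 1 and 2 are aged 18 to 55.
- Section 4.1 says "Cohort 2 will be initiated after interim or primary analyses of Cohort 1a".

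For classification, Section 9.3 says "All efficacy analyses will be done according to the as treated principle (ie, actually received vaccinations". Section 9.7 censors efficacy data at unblinding or at an unscheduled vaccine, whichever is first. Section 9.4.4 leaves the detailed method for exploratory endpoints to the SAP.

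**The concern.** Randomisation makes vaccine and placebo recipients comparable within a cohort, not across the pooled study when the allocation ratio changes between cohorts. Cohort 2 is over-represented among active recipients. If its risk up to censoring differs from that of Cohorts 1 and 3, the pooled arms differ in baseline risk before the vaccine has done anything. There is reason to expect unequal risks: high-exposure jobs are barred in two cohorts only, ages differ, and Cohort 2 starts later, which changes both the epidemic period it meets and its time to unblinding. At stake is a preliminary VE figure that could be shifted in either direction by an amount no reader could recover from pooled counts.

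**Working it through.** **The plan's own figures.** Active recipients: 300 (1a) + 20 (1b) + 300 (Cohort 3) + 240 (Cohort 2) = 860. Placebo: 75 + 5 + 75 + 30 = 185. The total is 1,045, as in Table 1. The upper bounds for zero events in Section 9.2 also reproduce: 1 - 0.05^(1/75) = 3.9% and 1 - 0.05^(1/120) = 2.5%. They concern safety; no sample-size figure concerns efficacy.

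**Imbalance.** Cohort 2 is 240/860 = 27.9% of active and 30/185 = 16.2% of placebo recipients.

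**Crude pooled comparison.** Let Cohort 2 risk be k times that of Cohorts 1 and 3, with equal follow-up between arms within a cohort. The values of k are assumptions. With no vaccine effect,

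crude RR = [(620 + 240k)/860] / [(155 + 30k)/185].

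With a true VE common to all cohorts, the VE read is 1 - (1 - VE) × crude RR.

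| k | crude RR, no effect | VE read, true 0% | VE read, true 60% |
|---|---|---|---|
| 0.5 | (740/860)/(170/185) = 0.936 | +6.4% | 62.5% |
| 1 | 1.000 | 0% | 60% |
| 2 | (1100/860)/(215/185) = 1.101 | -10.1% | 56.0% |
| 3 | (1340/860)/(245/185) = 1.177 | -17.7% | 52.9% |
| 5 | (1820/860)/(305/185) = 1.284 | -28.4% | 48.7% |

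**Stratified by cohort.** The Mantel-Haenszel weights are 620 × 155/775 = 124 for Cohorts 1 and 3 together and 240 × 30/270 = 26.67 for Cohort 2. At k = 2 and true VE 60%, the numerator is 0.4 × (124 + 2 × 26.67) = 70.9 and the denominator is 124 + 2 × 26.67 = 177.3. The ratio is 0.40, so VE is 60%. Every numerator term is (1 - VE) times its denominator term, so the result holds for any k.

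**Does the as-treated rule add to this?** The first vaccination already makes a participant an active or a placebo recipient. Missing a second dose because of infection moves nobody across that line. With an assumed 1% risk before Day 57 and 5% after, an arm's risk is 0.01 + 0.99 × 0.05 = 5.95%, both as treated and as randomised.

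**Shift against precision.** Assume a 5% placebo attack rate and true VE 60%. Expected cases are 185 × 0.05 = 9.25 on placebo and 860 × 0.05 × 0.4 = 17.2 on vaccine. The standard error of log RR is √(1/9.25 + 1/17.2) = 0.41, so the 95% interval for VE is about 11% to 82%. At a 2% attack rate it is about -41% to 89%.

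**The case against.** The strongest objection is that the endpoint wording says which cases are counted and which groups are compared, not how VE is estimated. Section 9.4.4 leaves method to the SAP, and nothing in the protocol forbids a cohort-stratified rate. This stands in part: an unstratified estimate is how the endpoint reads, not a method the protocol states. But the endpoint is framed over the whole study and names no strata, and following it as written gives a confounded comparison.

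It also stands that the bias is conditional. The protocol gives no attack rates, and not excluding high-exposure jobs does not prove Cohort 2 is at higher risk. Its later start could leave less time before unblinding and fewer cases per person. A reader might infer that the pooled figure must understate the vaccine; at k = 0.5 it overstates it. At k = 2 to 3 the shift is 4 to 7 points at true VE 60%, small beside the likely interval. Censoring under Section 9.7 already limits differential follow-up after crossover.

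A reader might further infer that the as-treated rule biases efficacy. Section 7.1 stops vaccination when "Participant has a positive test result for SARS-CoV-2 infection during the study", and Section 8.1.2.2 adds "The participant will not receive further study vaccinations but should remain on study for follow-up with assessments of safety and immunogenicity". An early case in a two-dose arm might then be recounted as a one-dose case, making two doses look better. The documents do not support this as a finding. Section 3 lists no one- versus two-dose efficacy contrast. No rule merges interrupted two-dose participants into the one-dose arm. In Cohorts 1 and 3 the single-dose regimens have a placebo second injection that infection blocks too.

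**Conclusion.** The point holds in limited form. Read as written, the Ad26.COV2.S versus placebo efficacy comparison pools cohorts with different allocation ratios, and it is confounded by cohort whenever cohort risks differ. For k between 0.5 and 3, a null vaccine reads as VE between about +6% and -18%, and a true 60% as between about 63% and 53%. There is no bias at k = 1. These figures rest on assumed k, a common VE across cohorts and equal follow-up between arms within each cohort. The dose-2 block does not bias this contrast. Severity is minor: the objective is exploratory and preliminary, no formal testing is planned, and the sample size was not set for efficacy.

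**What to change.** State with the Section 3 endpoint, or in the SAP, that the Ad26.COV2.S versus placebo efficacy comparison uses cases per person-time up to the Section 9.7 censoring date, stratified by cohort (Mantel-Haenszel, or exact conditional Poisson if cases are few). As a precaution only, add that if efficacy by number of doses is ever examined, it will be analysed by randomised regimen, or restricted in both regimens to cases after Day 57 among participants uninfected at Day 57.

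The change needs wording and programming, with no new data. The downside is slightly wider intervals where strata are sparse. Cohorts 1a and 1b share an age range and a 4:1 ratio, so they can form one stratum without reintroducing the allocation imbalance.

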## HYPOTHESIS

No formal hypothesis testing is planned. Descriptive statistics will be used to summarize the safety, reactogenicity, and immunogenicity endpoints (see Section 9.4, Statistical Analyses).

## Ad Hoc Booster Vaccination

Following local approval of protocol Amendment 15, the following objectives are applicable for all eligible participants (see Section 8.7) that consent to receive a single ad hoc booster dose of  $5 \times 10^{10}$  vp Ad26.COV2.S. The ad hoc booster vaccination will be provided to participants who have previously received 1 or more doses of any COVID-19 vaccine (ie, the Ad26.COV2.S vaccine, an mRNA vaccine and/or another COVID 19 vaccine authorized for primary vaccination including protein, inactivated, and adenovector-based vaccines) if the last vaccination was  $\geq 6$  months ago.

Objectives	Endpoints
Primary 
 
To assess the safety and reactogenicity of Ad26.COV2.S at the <math>5 \times 10^{10}</math> vp dose level administered as ad hoc booster vaccination in healthy adults aged <math>\geq 18</math> to <math>\leq 55</math> years and in adults aged <math>\geq 65</math> years in good health with or without stable underlying conditions.
 
	
 
Solicited local and systemic AEs for 7 days after ad hoc booster vaccination.
 
Unsolicited AEs for 28 days after ad hoc booster vaccination.
 
SAEs and AESIs from ad hoc booster vaccination until the end of the study.
 

Secondary 
 
To obtain samples to evaluate potential thromboembolic events following ad hoc booster vaccination by obtaining platelet counts and sufficient extra sera for specialized studies at the day of booster vaccination and 28 days later.
 
	
 
Platelet count on the day of ad hoc booster vaccination and 28 days after ad hoc booster vaccination. Additional analysis on collected sera samples in case of potential thromboembolic events.
 

Exploratory 
 
To assess the humoral and cellular immune response to Ad26.COV2.S ad hoc booster dose.
 
	Humoral immune response assessment may include, and is not limited to: 
 
SARS-CoV-2 neutralization: SARS-CoV-2 neutralizing titers in serum measured by a virus neutralization assay (VNA [wild-type virus and/or pseudovirion expressing S protein]) against the original strain and emerging variants.
 
SARS-CoV-2-binding antibodies measured by ELISA: Analysis of antibodies binding to the SARS-CoV-2 S and RBD protein from the original strain and emerging variants.
 
Adenovirus neutralization.
 
Functional and molecular antibody characterization (eg, avidity, Fc receptor interaction, antibody isotyping).
 
Epitope-specificity characterization for B- and T cells.
 
Passive transfer: Analysis of immune mediators correlating with protection against
 

Objectives	Endpoints
	
experimental SARS-CoV-2 challenge in a suitable animal model.
 
In a subset of participants, cellular immune response assessment may include, and is not limited to:
 
 
• Th1 and Th2 immune responses as assessed by flow cytometry after SARS-CoV-2 S protein peptide stimulation of PBMCs and ICS including CD4+/CD8+, IFN<math>\gamma</math>, IL-2, TNF<math>\alpha</math>, IL-4, IL-5, IL-13, and/or other Th1/Th2 markers.
 

 
• To examine the immune response in vaccinated individuals after natural infection and to explore other potentially informative biomarkers (eg, those associated with more severe disease).
 
	
 
• Confirmation of SARS-CoV-2 infection by molecular testing
 
• SARS-CoV-2 neutralizing titers in serum measured by a VNA (wild-type virus and/or pseudovirion expressing S protein)
 
• SARS-CoV-2-binding antibodies measured by ELISA: Analysis of antibodies binding to the SARS-CoV-2 S protein
 
• Functional and molecular antibody characterization
 

